10.2 Reasons for discontinuation of IMP

10.2.1 Reasons for permanent discontinuation of IMP

Subjects will permanently discontinue IMP in the event of:

- Anaphylactic reaction or other severe systemic reaction to IMP injection.
- An AE that, in the opinion of the investigator or sponsor's medical expert, contraindicates further dosing.
- Diagnosis of a malignancy during the trial, excluding carcinoma in situ of the cervix, or localised squamous or basal cell carcinoma of the skin.
- Evidence of pregnancy (e.g. a positive pregnancy test).
- Any infection that is opportunistic, such as active tuberculosis and other infections whose nature or course may suggest an immuno-compromised status.
- Severe laboratory abnormalities:
 - Alanine aminotransferase (ALT) or aspartate aminotransferase (AST) values $>3\times\text{ULN}$ with total bilirubin $>2\times\text{ULN}$ (unless elevated bilirubin is related to Gilbert-Meulengracht Syndrome).
 - Confirmed AST or ALT $>5\times\text{ULN}$ for >2 weeks.

THIS DOCUMENT CONTAINS CONFIDENTIAL INFORMATION AND MUST NOT BE COPIED OR MADE AVAILABLE TO ANY THIRD PARTY WITHOUT THE PRIOR WRITTEN CONSENT OF THE LEO PHARMA GROUP

Data to be recorded in the eCRF

The primary reason for permanent discontinuation of IMP must be recorded in the medical records and on the end-of-treatment form in the eCRF where the following options are available:

- Adverse event (a specification must be provided).
- Death.
- Lost to follow-up.
- Withdrawal by subject.
- Withdrawal by parent/guardian (applicable for adolescent subjects).
- Lack of efficacy.
- Pregnancy.
- Other (a specification must be provided).

It will also be recorded whether the discontinuation of IMP was related to the COVID-19 pandemic.

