#### 5.1.2 Trial periods and date of permanent discontinuation of IMP

The treatment period will be defined as the time from exposure start to exposure end and the remaining time after exposure end will be defined as the safety follow-up period. SFU period is only applicable for subjects where last date of contact does not equal the date of exposure end.

Definition of date of permanent discontinuation of IMP, exposure start, and exposure end are given in [Panel 3](#).

THIS DOCUMENT CONTAINS CONFIDENTIAL INFORMATION AND MUST NOT BE COPIED OR MADE AVAILABLE TO ANY THIRD PARTY WITHOUT THE PRIOR WRITTEN CONSENT OF THE LEO PHARMA GROUP

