### Panel 3: Date of permanent discontinuation of IMP, exposure start and end

Time point	Definition
Date of permanent discontinuation of IMP*	
 
Defined as the latest date of early termination visit (if existing) or date of onset of latest AE leading to withdrawal of IMP, otherwise date of the last visit, excluding SFU visit.
 

Exposure start	
 
Date and time of first dose.
 

Exposure end	
 
Date of Week 16 visit (if existing) at time 23:59:00, otherwise date of permanent discontinuation of IMP (if existing) at time 23:59:00, otherwise date of last IMP administration at time 23:59:00.
 

\*) Only defined for subjects who have a reason for permanent discontinuation of IMP recorded.

**Abbreviations:** AE = adverse event, IMP = investigational medicinal product, SFU=safety follow-up

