#### Panel 4: Visit windows

Visit (target day)	Visit window (day is date of assessment minus date of first dose)
Week 2 (Day 14)	Day 8 to 21
Week · (Day $7 \cdot x$ , where $x = 4, 6, 8, \dots, 16$ )	Day $7 \cdot x - 6$ to $7 \cdot x + 7$
SFU	36-49 days after last dose

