### Panel 11: Changes to the analyses described in the protocol

Section in CTP	Description of change	Brief rational
14.2 Trial analysis sets	The description of the full analysis set, and the safety analysis set has been updated such that subjects should both be assigned to treatment and dosed.	The definition in the CTP did not specify subjects to be assigned to treatment, but only dosed.
14.2 Trial analysis sets	In addition to the analysis sets defined in the CTP, an analysis set, called "usability analysis set ", for analysing endpoints related to IMP self-injection has been defined. Furthermore	The analysis set is described in the CTP, but not named. To ease readability and communication it has been defined and named usability analysis set
14.2 Trial analysis sets	A SFU analysis set is added to the list of the analyses sets	To analyse endpoints and assessments related to safety during the SFU period
14.3.16 General principles	In addition to what is stated in the CTP, the lower and upper quartiles will be used to summarise continuous data.	To align outputs with previous trials in the Tralokinumab project.
14.3.16 General principles	Baseline definition is added.	To define the baseline data.
14.3.16 General principles	It has been specified that the Wilson method is used to calculate the confidence interval for the responder analyses, and the statistically method Student's t-CI is used to calculate the CI for the continuous endpoints.	To specify what method is used.
14.3.6 Estimand strategy	Definition of date of permanent discontinuation of IMP has been changed to latest date of early termination visit (if existing) or date of onset of latest AE leading to withdrawal of IMP, otherwise date of the last visit, excluding safety follow-up visit rather than date of last IMP administration.	Definition in the CTP was erroneous.
14.3.3 Exposure and treatment compliance	From exposure start to end, not date of disc. of IMP. Presented both as continuous data and categorical.	End of exposure definition in CTP was erroneous.
14.3.7 Analysis of primary endpoints	Added a subgroup analysis for the primary endpoints (EASI75 at Week 16 and IGA 0/1 at Week 16). Each endpoint will be analysed by baseline IGA.	To look into subgroups.
14.3.4 Rescue medication	Definition of rescue medication has been updated to include upadacitinib and abrocitinib as preferred name.	The two treatments have been approved in the meantime.

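### For a discontinuer with no early termination visit on or after the last dose, SAP Panel 3 can date permanent discontinuation, and without a Week 16 visit exposure end too, before a documented dose

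*SAP*

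**What the plan says.** SAP Panel 3 gives the date of permanent discontinuation in steps. It is "Defined as the latest date of early termination visit (if existing") or the "date of onset of latest AE leading to withdrawal of IMP, otherwise date of the last visit, excluding SFU visit". A footnote limits this date: "Only defined for subjects who have a reason for permanent discontinuation of IMP recorded".

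Exposure end, in the same panel, is the Week 16 visit if there is one, then the date of permanent discontinuation, and only after that, "otherwise date of last IMP administration at time 23:59:00". SAP 5.1.2 adds that "the remaining time after exposure end will be defined as the safety follow-up period". SAP 5.2 computes patient-years from exposure start to exposure end, and SAP 5.7 reports safety separately for the two periods.

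Protocol 14.3.6 dated discontinuation at the last IMP administration. SAP Panel 11 replaces that date as erroneous. For the exposure rule in Protocol 14.3.3 it says "End of exposure definition in CTP was erroneous". In neither place is the last dose kept as a minimum.

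**The concern.** The onset of an adverse event is not the day on which IMP stopped. An event can begin, persist at the same severity through further two-weekly doses, and lead to withdrawal later. Protocol 10.2.1 has a criterion of this kind: the one that begins "Confirmed AST or ALT" applies only after more than two weeks, which is longer than one dosing interval.

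The last-visit fallback has a similar gap. Doses at Weeks 6, 8, 10 and 14 are taken at home from stock handed out earlier. Telephone visits have a window of ±3 days, so a home dose can follow the last contact.

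At stake is the period to which a subject's time and events belong. An injection site reaction after a later dose would appear in the follow-up tables although the subject was still being dosed. Under SAP 1.1 and 5.5.2, efficacy scores after the discontinuation date count as non-response in the by-visit responder tables, so scores taken on treatment can be overwritten.

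**Working it through.** The plan gives no figure to reproduce. The check applies Panel 3 as written to constructed subjects. Days are counted from the first dose.

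**Rules used**
- Discontinuation date D = later of early termination (ET) visit and AE onset, if either exists; otherwise the last visit other than safety follow-up (SFU). The wording could also be read as a strict order (ET visit, then AE onset, then last visit). The cases below come out the same either way.
- Exposure end E = Week 16 visit, otherwise D, otherwise last dose L.
- Gap = L − E. With a minimum at last dose, E* = max(E, L).
- Patient-years (PY) moved = gap / 365.25.
- Planned total, assuming 130 subjects with 16 weeks each: 130 × 112 / 365.25 = 39.86 PY.

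**Affected cases (no ET visit, no Week 16 visit, reason recorded)**

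| Case | E = D | L | Gap (days) | PY moved | Share of planned total |
|---|---|---|---|---|---|
| A: AE onset Day 20, severity unchanged, doses to Day 42 | 20 | 42 | 22 | 0.060 | 0.15% |
| A2: liver abnormality first seen and recorded as an AE on Day 28, dose on Day 42, criterion met after that | 28 | 42 | 14 | 0.038 | 0.10% |
| B: Week 10 call on Day 67, home dose Day 70, no AE | 67 | 70 | 3 | 0.008 | 0.02% |
| C: last non-SFU visit Day 28, home doses Days 42, 56 and 70, log returned at SFU visit | 28 | 70 | 42 | 0.115 | 0.29% |

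With the minimum, E moves to L in each row.

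**Controls**
- Case A with an ET visit on Day 50: D = E = 50, after the last dose. No change.
- Case A with a Week 16 visit on Day 112: E = 112 is unaffected, but D = 20 is still 22 days before the last dose.
- Last dose Day 42, no reason recorded and no Week 16 visit: E = L = 42. No change.

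**Several subjects.** The documents do not say how many subjects would be affected. If it were 7 of 130, the share is 7 × 3 / (130 × 112) = 0.14% to 7 × 42 / (130 × 112) = 2.02%. If it were 13, it is 0.27% to 3.75%. The upper ends assume that every affected subject has the 42-day gap.

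**Effect on other outputs**
- Adverse events: in Case A, events that start after Day 20 and up to the Day 42 dose go to the SFU tables. The event that led to withdrawal stays in the treatment period, because exposure end is set to 23:59 on its onset day.
- By-visit responders: IGA and EASI are scheduled after baseline only at Weeks 4, 12 and 16. In Case A the Day 28 score falls after D = 20 and becomes non-response; with D = 42 it would count as observed. In A2 no scheduled IGA or EASI falls between Days 28 and 42. In B and C no scheduled score follows the last visit. This effect therefore comes mainly from the AE-onset step.
- Week 16 primary endpoints: in Case A, D = 20 and D = 42 are both before Day 112. The subject is a non-responder under either date.

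**The case against.** The case against is mostly about reach, and much of it stands.

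- Protocol 10.3 asks every subject who stops IMP to attend an ET visit promptly after the last dose. If that visit takes place, Panel 3 gives a date on or after the last dose. The problem needs a missed visit.
- Protocol Appendix 2 has a worsening AE recorded as a new AE with its own onset. Only an event that persists without worsening keeps its early date.
- Telephone visits fall in the home-dosing weeks, so a subject who keeps them has a gap of a few days. Home doses are entered at the next site or telephone visit (Protocol 9.8.4). A dose after the last non-SFU visit will usually be known only if the log comes back at the SFU visit. For a subject who is truly lost, there may be no recorded dose to use.
- The analysis data reviewer's guide and define.xml hold further derivation rules and were not available. They may contain a date check.
- A minimum at last dose is not full parity. Completers are credited about 14 days after the Week 14 dose; an affected discontinuer would be credited none.

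These points limit the number of subjects and the size of the effect. None of them supplies the missing minimum in Panel 3, which is the SAP's own definition.

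A reader might also see a defect in the follow-up clock, because the SFU period can start before the last dose while the SFU visit falls "36-49 days after last dose". The documents do not support that as a separate fault. For every completer too, exposure ends at Week 16 while the SFU visit is timed from the Week 14 dose.

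**Conclusion.** The point holds in conditional form. It applies to a subject with a recorded discontinuation reason, no ET visit on or after the last dose, and a documented dose after the AE onset or last visit that Panel 3 uses. In that subject the discontinuation date is too early. Exposure end is too early as well only if there is no Week 16 visit.

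The size is small overall: about 0.02% to 0.29% of planned patient-years per affected subject, for constructed gaps of 3 to 42 days. The number of affected subjects is not known and is probably low.

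Two stronger inferences should not be drawn. The Week 16 primary results do not move, because these subjects are non-responders under either date. Adverse events are not lost and remain treatment-emergent, since SAP 5.7.1 tests only whether they started after first use of IMP; they are reported, but under the wrong period.

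The change is still worth making. This is a stated rule that can give a wrong date, and the affected subjects include those who stopped because of an adverse event, where attribution to a period matters most.

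**What to change.** In SAP Panel 3, define both the date of permanent discontinuation and exposure end as the later of the date now derived and the date of last IMP administration on the end-of-treatment form (Protocol 11.8). Panel 2 restates exposure end in the SFU analysis set; have it refer to Panel 3. Record the change in Panel 11.

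The cost is one clause and one line of derivation code, with no new data. Subjects whose derived dates already fall on or after the last dose are unchanged. The edit concerns analysis dates only and does not touch treatment or stopping rules.

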10.3 Early termination assessments

Permanent discontinuation of IMP

Subjects who permanently discontinue IMP for any reason will be asked to attend:

- Early termination visit as soon as possible after last administration of IMP.
- Safety follow-up visit (6 weeks after the last IMP administration).

See the schedule of trial procedures (Section 4) for data to be collected at these visits. The investigator will review any AEs which will be followed up according to Section 13.7, if the subject agrees.

Withdrawal from trial

Subjects who withdraw from the trial for any reason will be asked to attend an early termination visit as soon as possible after last administration of IMP (see the schedule of trial procedures [Section 4] for data to be collected at an early termination visit). The investigator will review any AEs which will be followed up according to Section 13.7, if the subject agrees.

Details on data to be recorded in the eCRF for subjects who withdraw from the trial can be found in Section 11.8.

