11.8 End-of-trial

End-of-treatment form

An end-of-treatment form will be completed in the eCRF for all subjects when they have had their last administration of IMP. This form will also be completed for subjects who permanently discontinue IMP and subjects who withdraw from trial (see Section 10.3 for early termination assessments).

The following data will be collected on the end-of-treatment form:

- Date of last IMP administration.
- Did the subject permanently discontinue IMP before Week 14? If yes, the primary reason for permanent discontinuation of IMP must be recorded (see Section 10.2.1).

End-of-trial form

An end-of-trial form must be completed in the eCRF for all assigned subjects. The end-of-trial form will be completed when the subject has had their last visit (that is, the safety follow-up visit, or early termination visit.)

The following data will be collected:

- Date of last contact.
- Did the subject attend the safety follow-up visit? If not, primary reason for not attending safety follow-up visit must be recorded (AE, death, lost to follow-up, withdrawal by subject, withdrawal by parent/guardian, lack of efficacy, pregnancy, or other). If 'AE' or 'other' is selected, a specification must be provided.

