## 1.1 Trial objectives, estimands, and endpoints

Objectives	Endpoints
Primary objective	Primary endpoints 
 
IGA score of 0 (clear) or 1 (almost clear) at Week 16.
 
EASI75 at Week 16.
 

Secondary objective	Secondary endpoints 
 
Number of treatment-emergent AEs from baseline to Week 16.
 
Presence of treatment-emergent ADA from baseline to Week 16.
 

Other objectives	Other endpoints 
 
Successful IMP self-administration when observed at the clinic at Week 4.
 
Successful IMP self-administration when administered at home at Week 8.
 

To evaluate the efficacy of tralokinumab administered by an autoinjector on severity and extent of AD, itch, and HRQoL in treating moderate-to-severe AD.	Other endpoints 
 
EASI90 at Week 16.
 
EASI50 at Week 16.
 
Percentage change in EASI score from baseline to Week 16.
 
Change in POEM from baseline to Week 16.
 
Reduction in POEM of at least 4 from baseline to Week 16/Reduction in POEM of at least 6 from baseline to Week 16.
 
Change in DLQI/CDLQI from baseline to Week 16.
 
Reduction in DLQI of at least 4 from baseline to Week 16/Reduction in CDLQI of at least 6 from baseline to Week 16.
 
Change in Eczema-related Weekly Sleep NRS from baseline to Week 16.
 
Change in Worst Weekly Pruritus NRS/Adolescent's Pruritus NRS from baseline to Week 16.
 
Reduction of Worst Weekly Pruritus NRS/Adolescent's Pruritus NRS of at least 4 from baseline to Week 16.
 

- Only adult subjects with a score of 4 and above and adolescent subjects with a score of 6 and above at baseline will be included in the analysis.
- For adult subjects, a response is defined as a reduction of at least 4 from baseline. For adolescent subjects, a response is defined as a reduction of at least 6 from baseline.
- Only subjects with Worst Weekly Pruritus NRS/Adolescent's Pruritus NRS score of 4 or above at baseline will be included in the analyses.

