## 5.5 Secondary and other endpoints analyses

The secondary endpoint, number of treatment-emergent AEs from baseline up to Week 16, and the analysis of this is covered in Section [5.7.1](#).

The secondary endpoint, presence of treatment-emergent ADA from baseline to Week 16, and the analysis of this is covered in Section [5.6](#).

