## 5.7 Safety analysis

The analysis of safety will be presented separately for the treatment period and SFU period.

Details on incomplete dates, duplicate measurements, unscheduled visits can be found in the ADRG or Define.xml.

THIS DOCUMENT CONTAINS CONFIDENTIAL INFORMATION AND MUST NOT BE COPIED OR MADE AVAILABLE TO ANY THIRD PARTY WITHOUT THE PRIOR WRITTEN CONSENT OF THE LEO PHARMA GROUP

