### 5.7.1 Adverse events

AEs will be coded during the course of the trial according to Medical Dictionary for Regulatory Activities (MedDRA) version 24.0 and presented as described in the CTP section 14.3.12.1.

An AE will be considered treatment emergent if started after the first use of IMP. Only treatment emergent AEs will be summarized and tabulated.

AEs will be presented by preferred terms (PT) and primary system organ class (SOC).

An overall summary of the number (percentage) of AEs, the rate of AEs (number of AEs per 100 patient years of observation time), and the number (percentage) of subjects with any treatment-emergent AEs, death, SAEs, AEs leading to premature discontinuation from IMP and/or withdrawals from the trial, treatment-related AEs, and severe AEs will be presented. In addition, AEs will be presented by severity and causal relationship to IMP.

A summary of all AESIs will be tabulated, and for the AESI injection site reactions, a separate severity grading derived from the data collected according to [Panel 9](#) will be tabulated as described in Section [5.7.2](#)

The number (percentage) of AEs, rate of AEs, and number of subjects with each type of AEs will be tabulated.

SAEs and AESIs will be evaluated separately. A narrative for each SAE will be given.

All AEs recorded during the course of the trial will be included in subject data listings.

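### For subjects with no Week 16 visit, the SAP's treatment period closes before Week 16, so its AE table understates the secondary endpoint, which runs to Week 16

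*SAP*

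**What the plan says.** The endpoint has a fixed window. SAP 1.1, like Protocol section 6, lists "Number of treatment-emergent AEs from baseline to Week 16", with no exception for subjects who stop early. SAP 5.5 keeps that window and passes the analysis on: "number of treatment-emergent AEs from baseline up to Week 16, and the analysis of this is covered in Section" 5.7.1. Section 5.7.1 sets a start but no end: "An AE will be considered treatment emergent if started after the first use of IMP".

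The tabulation follows a different clock. SAP 5.7 states: "The analysis of safety will be presented separately for the treatment period and SFU period". SAP Panel 2 assigns the safety analysis set to safety endpoints in the treatment period and a separate SFU set to the time afterwards. SAP 5.1.2 draws the line between them, with everything beyond that line counted under follow-up: "The treatment period will be defined as the time from exposure start to exposure end and the remaining time after exposure end will be defined".

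Panel 3 gives exposure end in three steps: "Date of Week 16 visit (if existing) at time 23:59:00, otherwise date of permanent discontinuation of IMP (if existing) at time 23:59:00, otherwise date of" the last IMP dose. The discontinuation date in the second step is the later of the early-termination visit and the onset of the last AE that caused IMP to be withdrawn. If neither exists, it is the last visit other than the SFU visit. It is defined only when a discontinuation reason has been recorded.

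Two protocol rules determine who is affected. Protocol 10.3 asks subjects who stop IMP for two visits: "Early termination visit as soon as possible after last administration of IMP", and a safety follow-up visit 6 weeks after the last dose. The end-of-treatment form in Protocol 11.8 asks: "Did the subject permanently discontinue IMP before Week 14? If yes, the primary reason for permanent discontinuation of IMP must be recorded".

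**The concern.** The endpoint stops at a calendar point, but the treatment period stops at an event. For a subject who attends Week 16 the two coincide. For anyone else the treatment period can close weeks earlier, while AEs are still being collected and Week 16 has not been reached. Those AEs belong to the stated endpoint but are presented as follow-up events, mixed with what completers report between Weeks 16 and 20.

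If the treatment-period table is reported as the secondary endpoint, the number of AEs and the percentage of subjects with an AE are too low. The shortfall comes only from subjects who stopped early or missed Week 16. SAP Panel 11 records the new SFU set and the changed definition of exposure end. Its row for the protocol's AE section deals only with the percentage of AEs. Nothing there tells a reader that the period split affects the secondary endpoint.

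**Working it through.** The plan gives no figure for this point. Its only precision figures (standard errors of 3.44% and 3.98% at 130 subjects) do reproduce, but they concern the primary endpoints and have no bearing here.

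**Inputs from the documents**
- Week 16 is Day 112, counted from the first dose (SAP Panel 4).
- The last planned dose is at Week 14, Day 98 (Protocol 7.1).
- Follow-up is 6 weeks, 42 days, after the last dose (Protocol 10.3).
- The planned number of subjects is 130 (Protocol 14.1).

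**Assumptions, not in the documents**
- The early-termination visit falls *d* = 7 days after the last dose (range 3 to 14) and sets the discontinuation date.
- The subject is observed until the follow-up visit at 42 days.
- 10% of subjects stop early (range 5% to 20%).

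**Per subject.** With the last dose on Day *L*, observed time up to Week 16 ends on Day min(112, *L* + 42), and exposure end is Day *L* + *d*. Days moved to the SFU table = min(112, *L* + 42) − (*L* + *d*).

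| Last dose | Observed days to Day 112 | Moved, d = 3 | Moved, d = 7 | Moved, d = 14 | Share at d = 7 |
|---|---|---|---|---|---|
| Week 0 (Day 0) | 42 | 39 | 35 | 28 | 83% |
| Week 4 (Day 28) | 70 | 39 | 35 | 28 | 50% |
| Week 10 (Day 70) | 112 | 39 | 35 | 28 | 31% |
| Week 12 (Day 84) | 112 | 25 | 21 | 14 | 19% |

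For the Week 4 row the share runs from 28/70 = 40% to 39/70 = 56%. An early-termination visit on the day of the last dose gives the ceiling of 42 days for any last dose up to Week 10.

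**Week 14 dose taken, Week 16 missed, Week 20 attended.** The form asks about stopping before Week 14, so no reason is recorded and no discontinuation date exists. Panel 3 falls through to the last dose, Day 98. Days moved = 112 − 98 = 14, namely Days 99 to 112. The same days count as treatment period for a subject who attended Week 16.

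**Aggregate, under the assumptions.** 10% of 130 is 13 early stoppers. 13 × 35 = 455 days, and 455 / 365.25 = 1.25 patient-years. The other 117 contribute 117 × 112 = 13,104 days, or 35.9 patient-years. If each early stopper is observed for 12 weeks (last dose at Week 6), the total is 13,104 + 13 × 84 = 14,196 days, and 455 / 14,196 = 3.2%.

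Varying the stopping rate from 5% to 20% and the time moved from 2 to 6 weeks per early stopper:
- Low end: 6.5 × 2 = 13 person-weeks of 123.5 × 16 + 6.5 × 12 = 2,054, or 0.6%.
- High end: 26 × 6 = 156 person-weeks of 104 × 16 + 26 × 12 = 1,976, or 7.9%.

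The documents give no AE rate, so the number of AEs moved cannot be calculated.

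**The case against.** The strongest reply is that the SAP never says the secondary endpoint equals the treatment-period table. Section 5.5 still says up to Week 16, 5.7.1 has no end cut-off, and the protocol section it refers to (14.3.12.1) has no period split. Table shells are not in the documents, and derivation rules are left to files that are not available here. This stands as a limit on certainty. Equating the two is the natural reading of SAP 5.7 with Panel 2, but it is an inference, and one cannot assert that no output will show the endpoint's own window. It does not remove the problem: the only period rules that the SAP states give a different window from the endpoint's.

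Several stronger readings might be inferred, and the documents do not support them:
- *That AEs are lost.* They remain treatment-emergent, are presented under the SFU set and appear in the subject listings.
- *That all AEs before Week 16 in early stoppers are affected.* Only those starting after exposure end move.
- *That the AEs which caused stopping are hidden.* Panel 3 takes the later of that AE's onset and the early-termination visit, so such an AE normally stays in the treatment period.
- *That the AE rate is biased.* If events and observation time are cut at the same point, numerator and denominator match. The counts and the percentage of subjects are what change.

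It is also fair to say that separating on-treatment from follow-up AEs is a recognised presentation and that no test or comparison depends on it. The day counts are upper values too. Protocol 10.3 asks subjects who withdraw from the trial only for the early-termination visit, whereas footnote 4 of the schedule of procedures says all subjects have a final follow-up visit. A subject with no later contact contributes few or no moved days.

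**Conclusion.** The mismatch is real and more than missing detail: following the stated period rules yields a count that is not the stated endpoint for subjects without a Week 16 visit. Per subject it can be substantial, at up to 35 observed days for a last dose by Week 10 (28 to 39 across the assumed delays) and 14 days for a subject who takes the Week 14 dose and misses Week 16. Across the trial it is probably a few percent of person-time. That range rests on assumed stopping rates and visit timing, and the effect in numbers of AEs is unknown.

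The conclusion is limited to classification. The treatment-period count and percentage of subjects understate the baseline-to-Week 16 endpoint, and Panel 11 does not disclose it. The documents do not support a conclusion that safety data are discarded or that the AE rate is wrong.

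**What to change.** In SAP 5.5 and 5.7.1, add one tabulation for the secondary endpoint. It should cover treatment-emergent AEs in the safety analysis set with onset from the first dose to the Week 16 visit or, if that visit was not attended, to Day 112 or last contact, whichever is earlier, regardless of IMP discontinuation. Patient-years for this table should be cut at the same point.

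Add a row to Panel 11 saying that the treatment-period AE tables end at exposure end and may therefore differ from the secondary endpoint.

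Keep the treatment-period and SFU tables as planned, and keep Panel 3 as the definition of drug exposure. Recasting all main AE tables on a calendar cut is a matter of preference and is not needed.

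The cost is one definition, one AE flag and one extra table, with no new data. The downside is slightly higher AE counts for early stoppers than the treatment-period table shows.
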